3.2.2 Secondary endpoints

- Incidence of AE and SAE assessed as per CTCAE 4.03, laboratory measurements, ECG, vital signs, and other safety endpoints
- OS, 6-month OS rate, and PFS, TTR, DoR, and DCR evaluated as per RECIST v1.1
- Immunogenicity evaluation: positive rates of ADA and NAb

3.2.3 Exploratory endpoint

- Tumor biomarkers (including but not limited to expression levels of PD-L1 and TMB in tumor samples)

[figure not shown]
4 STUDY DESIGN

This is a randomized, open-label, multi-center phase II clinical study. Eligible subjects after screening will be randomized into the following 3 groups in a 1:1:1 ratio, with 4 weeks as a treatment cycle. Refer to [Figure 2](#) for the study design. Refer to [Figure 3](#) for the study process.

The study consists of two stages. In Stage I, subjects will be randomized into 3 different dose groups, with 6 subjects in each group. It is planned that after the last subject in Stage I completes Cycle 1 treatment (28 days), the leading center's principal investigator and the sponsor will jointly perform a safety assessment of subjects enrolled in Stage I, decide the treatment group of Stage II, and choose one group of method of administration and a tolerated dose of apatinib for Stage II treatment.

A total of 39 subjects will be enrolled in Stage II. The primary analysis will be performed when the last subject has been treated for 180 days.

For any treatment group entering Stage II, if the safety is acceptable and the efficacy meets the corresponding statistical criteria, it indicates potential needs of further development.

Note: Subjects with PD for the first time must be confirmed; for medication after the initial PD, refer to Section 6.1.2 of the protocol; for imaging confirmation and subsequent evaluation of the initial PD, refer to Section 8.1.2 of the protocol

Figure 2. Design of the phase II study of SHR-1210 combined with apatinib

[figure not shown]

Figure 3. Process of the study of SHR-1210 combined with apatinib

5 STUDY POPULATION

5.1 Inclusion Criteria

Patients must meet all of the following inclusion criteria to be eligible for this study.

1. All patients must sign an ICF prior to starting any study-related procedures
2. Aged ≥ 18 and ≤ 70 years
3. Histologically or cytologically confirmed small cell lung cancer
4. Staged ED-SCLC according to VALG staging
5. Have previously received first-line platinum-based treatment for ED-SCLC and have shown objective imaging progression. Including:
 - Sensitive recurrence: progression in ≥ 90 days from the last chemotherapy
 - Drug-resistant recurrence: progression during chemotherapy or within 90 days from the last chemotherapy
6. Able to provide tumor tissue samples for diagnosis, either archived samples within 12 months prior to the first dose of study drug or freshly obtained. The specimens shall meet the requirements of formalin-fixed and paraffin-embedded (FFPE) tumor tissue blocks allowing the cutting of at least 5-10 slices with a thickness of 4-6 μm for staining and testing. Cell smears from fine needle aspiration or centrifuged pleural fluid, bone lesions without soft tissue components or decalcified bone tumor specimens, and drill biopsy tissues are not acceptable, as they are insufficient for biomarker detection
7. ECOG PS of 0-1
8. Life expectancy of ≥ 8 weeks
9. With at least one target lesion without previous radiotherapy (RECIST v1.1) shown by CT or MRI scan ≤ 28 days prior to the first dose of study drug
10. Males and females of reproductive potential must take contraceptive measures from the first dose of study drug to within 24 weeks after the last dose of study drug (see 6.6.2 of the protocol for recommended contraceptive methods)
11. Had no transfusion of blood or blood products within 14 days prior to the first dose, not corrected with G-CSF or other hematopoietic colony-stimulating factors. Before the first dose of study drug, laboratory test values must meet the following conditions:
 - (1) Hematology: $\text{WBC} \geq 3.0 \times 10^9/\text{L}$; $\text{ANC} \geq 1.5 \times 10^9/\text{L}$; $\text{PLT} \geq 100 \times 10^9/\text{L}$; $\text{HGB} \geq 9.0 \text{ g/dL}$

- (2) Liver function: AST $\leq 2.5 \times$ ULN, ALT $\leq 2.5 \times$ ULN for patients without liver metastasis; ALT and AST $< 5 \times$ ULN for patients with liver metastasis; TBIL $\leq 1.5 \times$ ULN (TBIL < 3.0 mg/dL in patients with Gilbert syndrome); and ALB ≥ 3 g/dL
- (3) Renal function: Cr $\leq 1.5 \times$ ULN or CrCl ≥ 40 mL/min (using Cockcroft/Gault formula, see Appendix 2); negative UPRO
- (4) Coagulation function: INR ≤ 1.5 , APTT $\leq 1.5 \times$ ULN
- (5) Others: Lipase $\leq 1.5 \times$ ULN. Patients with lipase $> 1.5 \times$ ULN without clinical or radiographic evidence of pancreatitis may be enrolled; Amylase $\leq 1.5 \times$ ULN. Patients with amylase $> 1.5 \times$ ULN without clinical or radiographic evidence of pancreatitis may be enrolled. ALP $\leq 2.5 \times$ ULN; for patients with bone metastases, ALP $\leq 5 \times$ ULN

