6.4.3 SHR-1210

Dose increase or reduction for SHR-1210 is prohibited. Only interruption or permanent discontinuation is allowed. Dose interruption of SHR-1210 is allowed for up to 8 weeks (from the actual time of last dose); otherwise the treatment of SHR-1210 shall be discontinued. For SHR-1210 interruption that exceeds 8 weeks, the investigator should discuss with the sponsor's medical department if he/she judges that the subjects can benefit from continued treatment.

Refer to [Table 8](#) for the requirements on dose modification of SHR-1210. Refer to Appendix 6 for the guidelines on dose modifications and handling of toxicities of SHR-1210. Refer to [Table 9](#) for the treatment of SHR-1210 related infusion reactions.

In addition, treatment should be discontinued permanently if PD is determined by the investigator as per the RECIST v1.1 criteria (unless subjects meet the criteria for continued treatment after PD as described in Section 6.1.2 of the protocol). For treatment interruption due to medical events, surgeries, or unexpected (holidays) events unrelated to the study treatment, the subject should resume study treatment within 2 weeks after interruption (i.e., originally scheduled administration time), unless otherwise jointly determined by the investigator and the sponsor. The reasons for treatment interruption should be documented in the eCRF.

Table 8. Principles for SHR-1210 dose modification

Adverse Drug Reaction	Severity	Dose Modification
Pneumonia	Grade 2 pneumonia	Treatment interruption ^a
	Grade 3 or 4 pneumonia	Permanent discontinuation
Diarrhea/Enterocolitis	Grade 2 or 3 diarrhea or enterocolitis	Treatment interruption ^a
	Grade 4 diarrhea or enterocolitis	Permanent discontinuation
Dermatitis	Grade 3 dermatitis	Treatment interruption ^a
	Grade 4 dermatitis	Permanent discontinuation
Hepatitis	For subjects with normal baseline ALT, AST, or TBIL, Grade 2 AST, ALT, or TBIL increased, or For subjects with baseline AST, ALT, or TBIL > ULN, AST, ALT, or TBIL increased by ≥ 50% persisting for < 7 days	Treatment interruption ^a
	For subjects with normal baseline ALT, AST, or TBIL, Grade 3 or 4 AST, ALT, or TBIL increased, or For subjects with baseline AST, ALT, or TBIL > ULN, AST, ALT, or TBIL increased by ≥ 50% persisting for ≥ 7 days	Permanent discontinuation
	Grade 2 hypophysitis	Treatment interruption ^b
	Grade 3 or 4 hypophysitis	Permanent discontinuation

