8.2 Safety Evaluation

8.2.1 Routine laboratory safety evaluation

Table 15. Routine laboratory safety evaluation

Hematology	RBC, HGB, HCT, WBC, PLT, LYM, ANC, MONO, EOS, and BASO
Coagulation Function	TT, PT, APTT, and INR
Clinical Chemistry	TBIL ^a , ALT, AST, γ -GT, ALP, ALB, TP, LDH, BUN, Cr, Na, K, Cl, Mg, Ca, P, lipase, amylase, and FBG
Urinalysis	PH, UALB, UPRO ^b , URBC ^c , and UGLU
Routine Stool Test	Occult blood

^a. If TBIL $\geq 2 \times$ ULN (without evidence of Gilbert syndrome), then direct bilirubin and indirect bilirubin shall be tested separately.

^b. The white blood cells should be examined microscopically (if appropriate), and the red blood cells should be examined with a high-power field of view.

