9.2.4 Potential drug-induced liver injury

Drug-induced liver injury will be considered if AST and/or ALT levels are abnormal accompanied with abnormal elevation of total bilirubin, the following criteria are met, and when there are no other causes of liver injury. These cases should always be considered as important medical events.

Potential drug-induced liver injury is defined as follows:

Baseline Period	Normal (AST/ALT and TBIL)	Abnormal (AST/ALT and TBIL)
Treatment Period	
ALT or AST $> 3 \times$ ULNwith TBIL $\geq 2 \times$ ULNand ALP $\leq 2 \times$ ULNand no hemolysis	
AST or ALT $\geq 2 \times$ baseline level, and values $\geq 3 \times$ ULN; or AST or ALT $\geq 8 \times$ ULNwith TBIL increase $\geq 1 \times$ ULN or TBIL $\geq 3 \times$ ULN

After being notified of the abnormal results, the subjects should return to the study center for an assessment as soon as possible (preferably within 48 h). Assessments include the laboratory tests, detailed medical history, and physical assessment, and the possibility of hepatic tumor (primary or secondary) should be considered.

Except for the reexaminations of AST and ALT, albumin, creatine kinase, TBIL, direct and indirect bilirubin, γ -GT, prothrombin time (PT)/international normalized ratio (INR), and ALP should also be examined. Detailed medical history should include history of alcohol use, acetaminophen, soft drugs, various supplements, family diseases, occupational exposure, sexual behavior, travel, contact with jaundice patients, surgery, blood transfusion, hepatic diseases, and allergies. Further tests may include the testing for acute hepatitis A, B, C and E, and hepatic imaging (such as biliary tract). If the above laboratory criteria are confirmed upon re-examination, the possibility of potential drug-induced liver injury should be considered in the absence of any other causes of abnormal liver function, without waiting for all liver function test results. Potential drug-induced liver injury should be reported as an SAE.

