Appendix 6 Guidelines on Dose Modifications and Handling of Toxicities of SHR-1210

	AE Grading/Dose Modification		Treatment of Toxicity
General Rules	AEs are graded per the NCI CTCAE v4.03; if it is judged as an irAE, please refer to this guideline.		The guidelines described in this table are recommended for the treatment of irAEs.
	Grade 1	Dose modification is not required.	
 Subjects should be comprehensively evaluated to rule out any alternative causes (such as progressive disease, concomitant medication, infections, etc.) When there is no clear alternative cause and glucocorticoid therapy is needed, it should be judged as an irAE.
	Grade 2	Treatment interruption 
 If aggravated, treat as Grade 3 or 4 If improved to Grade 0-1 or baseline, continue the treatment on the next scheduled treatment date 	
 For low-grade (Grade 1 or 2 unless otherwise specified) events, symptomatic and local treatment should be considered. For persistent low-grade events (Grade 1 or 2) or severe (Grade ≥ 3) events, systemic glucocorticoid therapy should be considered. If recurrence or deterioration occurs during the dose tapering of glucocorticoids, the dose of glucocorticoids should be increased until the symptoms are stable or improved, and then the dose of glucocorticoids should be tapered at a lower rate.
	Grade 3	Treatment interruption or permanent discontinuation	
 Once sustained clinical improvement is observed, subjects receiving intravenous glucocorticoids can switch to an equivalent dose of oral glucocorticoid therapy at the beginning of the dose tapering or earlier (the low bioavailability of oral glucocorticoids should be considered).
	Grade 4	Permanent discontinuation	
 For events where systemic glucocorticoid therapy is ineffective, a stronger immunosuppressive agent, such as TNF antagonists (e.g., infliximab) or mycophenolate mofetil, should be considered after discussing with the study physician. For local inflammatory reactions of Grade 3/4 lesions (such as local pain, irritation, and rashes) caused by potential tumor response, SHR-1210 may not be discontinued at the judgment of the investigator.

	AE Grading/Dose Modification		Treatment of Toxicity

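### The liver-injury definition in protocol 9.2.4 cannot be met by an eligible subject with normal AST/ALT and TBIL whose ALP enters and stays above 2 x ULN, so that subject loses its automatic SAE classification

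*Protocol*

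**What the plan says.** **Entry.** Protocol 5.1, item 11(5), and the synopsis allow "ALP $\leq 2.5 \times$ ULN; for patients with bone metastases, ALP $\leq 5 \times$ ULN". The AST/ALT and TBIL limits stand separately in item 11(2), so normal transaminases and bilirubin with a raised ALP are compatible with enrolment.

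**Definition.** Protocol 9.2.4 sorts subjects by whether baseline AST/ALT and TBIL were normal or abnormal. Baseline ALP plays no part.

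- Normal baseline: ALT or AST above 3 x ULN, TBIL at least 2 x ULN, ALP at most 2 x ULN, and no hemolysis. All four are required.
- Abnormal baseline: "AST or ALT $\geq 2 \times$ baseline level, and values $\geq 3 \times$ ULN", or AST or ALT at least 8 x ULN, together with a TBIL rise of at least 1 x ULN or TBIL of at least 3 x ULN. There is no ALP condition.

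Both columns apply only "when there are no other causes of liver injury".

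**Consequence.** A case that meets the definition is always to be treated as an important medical event, and "Potential drug-induced liver injury should be reported as an SAE". Section 9.2.6 then requires notice to the sponsor within 24 h. Section 9.2.4 also describes a recall, preferably within 48 h, and a list of further tests.

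**The concern.** The entry limit and the definition do not fit together. Item 11(5) expects some subjects, above all those with bone metastases, to start with ALP above 2 x ULN. In such a subject an ALP above 2 x ULN during treatment need not say anything about a new liver event, yet it blocks the definition.

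The table is also uneven. A subject who enters with raised ALP, AST/ALT and TBIL can qualify, because the abnormal-baseline column ignores ALP. A subject who enters with raised ALP alone cannot. The documents give no reason for the difference.

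At stake is uniform safety reporting. Two subjects with the same ALT and bilirubin course can be classified differently because of their ALP at entry: one is automatically an SAE, the other only if some other criterion or judgment makes it so. Safety is part of the primary objective (3.1.1), and the SAP plans no joint AST/ALT-and-bilirubin analysis that would pick up the second case later.

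**Working it through.** The plan states no figure to reproduce here. The check is one of logic, with all values in multiples of ULN.

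**Inputs**

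- ALP ceiling at entry: 2.5, or 5 with bone metastases (5.1, item 11(5)).
- Normal-baseline rule: ALT or AST > 3, TBIL >= 2, ALP <= 2, no hemolysis (9.2.4).
- Abnormal-baseline rule: as described above, without ALP (9.2.4).
- Planned subjects: 57 (protocol 10.1).

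**Step 1. Eligible range outside the definition.** ALP above 2 and up to 2.5 without bone metastases; above 2 and up to 5 with them.

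**Step 2. Apply the rules.** Take 20 on-treatment combinations, ALT 3.5, 5, 8, 10, 20 by TBIL 2, 3, 5, 10, with no hemolysis, no other cause, and ALP held at its entry value.

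| Column | Entry ALP | Combinations meeting the definition |
|---|---|---|
| Normal baseline | 1.1, 1.9, 2.0 | 20 of 20 |
| Normal baseline | 2.1, 2.5, 3, 4, 5 | 0 of 20 |
| Abnormal baseline (ALT 1.2, TBIL 1.1 at entry) | all eight values | 15 of 20 |

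The five misses in the last row are those with TBIL 2: the rise is 2 - 1.1 = 0.9, below the required 1, and 2 is below 3. They have nothing to do with ALP. The zero follows directly from the ALP clause, so the grid illustrates the rule and says nothing about frequency.

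**Step 3. Fall in ALP needed before the definition can be met.** Required fall = 1 - 2/(entry ALP).

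- Entry 2.1: 1 - 2/2.1 = 5%
- Entry 2.5: 1 - 2/2.5 = 20%
- Entry 3: 1 - 2/3 = 33%
- Entry 4: 1 - 2/4 = 50%
- Entry 5: 1 - 2/5 = 60%

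**Step 4. Number of subjects.** The documents give neither the share with this baseline nor a liver-injury rate, so both are assumptions.

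- Share 2%, 5%, 10%: 57 x 0.02 = 1.1; 57 x 0.05 = 2.9; 57 x 0.10 = 5.7 subjects.
- With a further assumed liver-injury rate of 1% to 5%: from 57 x 0.02 x 0.01 = 0.01 to 57 x 0.10 x 0.05 = 0.29 expected events, before removing those reported by another route.

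**Step 5. Test the proposed condition** (if baseline ALP > 2, require ALP < 2 x baseline).

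- ALP held at its entry value above 2: always below twice itself, so 20 of 20.
- ALP 2.1 rising to 10: the limit is 2 x 2.1 = 4.2, so not met. A plain waiver would count it.
- ALP 1.5 rising to 3: baseline is not above 2, so the existing limit applies and it is not met, as now.
- Baseline ALP at or below 2: nothing changes.

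**The case against.** **The ALP condition may be deliberate.** It sits beside the hemolysis condition, and both can serve to set aside other explanations for a bilirubin rise. That is a fair defence for subjects who enter at or below 2 x ULN. It is weak where the elevation predates the first dose, and the separate no-other-cause requirement already lets the investigator exclude cholestasis or progression.

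**Other rules cover most of the ground, none with an ALP condition.**

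- Table 8 stops SHR-1210 permanently for "For subjects with normal baseline ALT, AST, or TBIL, Grade 3 or 4 AST, ALT, or TBIL increased", and Table 7 governs apatinib.
- At TBIL of 2 x ULN or more without evidence of Gilbert syndrome, Table 15 says "then direct bilirubin and indirect bilirubin shall be tested separately".
- Appendix 6 says "When there is no clear alternative cause and glucocorticoid therapy is needed, it should be judged as an irAE". Its hepatitis guidance calls for discussion with the sponsor's medical department at Grade 3-4, and at Grade 2 without recovery in 3-4 days. A Grade 3 or higher immune-related event is reportable within 24 h under 9.4.
- Section 9.2.1 keeps the general SAE criteria, including other important medical events.
- Grade 3 or higher laboratory abnormalities that lead to intervention or hospitalization, or last at least 7 days, count in the primary safety endpoint (3.2.1).

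This stands and makes the remainder small: an event not judged immune-related (for example, attributed to apatinib), or graded below 3, that meets no other SAE criterion. For that event, reporting within 24 h depends on the investigator choosing to call it an important medical event. Section 9.2.4 removes that choice for other subjects.

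**A reader might infer that recall and work-up are lost too.** The text does not establish that. Section 9.2.4 links recall to notification of the abnormal results, lists ALP among the tests to be done on re-examination, and only afterwards speaks of the criteria being confirmed. On a fair reading, abnormal ALT and bilirubin prompt recall and work-up whatever the ALP.

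**Conclusion.** The point holds in a narrow form. An eligible subject with normal baseline AST/ALT and TBIL whose ALP enters and stays above 2 x ULN cannot meet the 9.2.4 definition, and no other clause supplies its automatic important-medical-event and SAE classification. This follows from the text alone and needs no assumption about frequency.

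The practical size is small: about 1 to 6 subjects with such a baseline under assumed shares of 2% to 10%, and well under one expected liver event under the further assumed rates of 1% to 5%. No number of missed reports can be claimed.

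A reader might infer that liver injury would go undetected. It would not: clinical chemistry, including ALP, is tested before each SHR-1210 dose after the first, with the baseline sample taken at screening (Table 1, note 8), and the dose rules act on the results. Nor does the point touch ORR or the sample size, and Stage I selection rests on listings of all AEs and laboratory results (SAP 6). It is worth correcting because the correction is cheap and safety is a primary objective.

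**What to change.** In the normal-baseline column of the 9.2.4 table, replace the ALP line with: *and ALP <= 2 x ULN (or, if baseline ALP is > 2 x ULN, ALP < 2 x baseline)*. Leave the ALT/AST, TBIL, hemolysis and no-other-cause conditions as they are. The factor of 2 mirrors the baseline-relative AST/ALT rule in the abnormal-baseline column and keeps a screen against a large new ALP rise. A plain waiver of the ALP condition when baseline ALP exceeds 2 x ULN is an acceptable alternative, since the abnormal-baseline column already has no ALP condition; it gives up that screen.

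One step remains: a subject going from 1.9 to 2.1 x ULN would still fail, while one steady at 2.1 would qualify. That is the price of leaving the rule untouched for everyone who enters at or below 2 x ULN.

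Cost: one clause in one protocol table. Baseline ALP is already collected, so no test or visit is added. The downside is a few more SAE reports, some of which may prove cholestatic or due to progression.

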5.2 Exclusion Criteria

Patients meeting any one of the followings are not eligible to participate in this study:

1. With histologically or cytologically confirmed mixed SCLC and NSCLC.
2. Patients who have previously received anti-tumor viral treatment. Patients who have previously received any T cell costimulation or immune checkpoint therapy, including but not limited to CTLA-4 inhibitors, PD-1 inhibitors, PD-L1/2 inhibitors, or other drugs targeting T cells.
3. Patients who have previously received anti-VEGF/VEGFR therapy.
4. Patients with clinically symptomatic brain metastasis or meningeal metastasis. Treated patients with brain metastasis should meet the following conditions to be enrolled:
 - No MRI-proven progression ≥ 4 weeks after the end of treatment
 - Completed treatment within ≥ 28 days prior to the first dose of study drug
 - No need to receive systemic corticosteroid treatment (> 10 mg/day prednisone or an equivalent dose) in ≤ 14 days prior to the first dose of study drug
5. Radiotherapy of the chest and whole brain should be completed less than 4 weeks prior to the first dose of study drug (patients whose palliative radiotherapy for bone lesions was completed prior to the first dose of study drug are allowed to be enrolled)
6. Clinically symptomatic effusion in the third space, such as pericardial effusion, pleural effusion, and ascites effusion that cannot be controlled by drainage or other treatments

7. Active, known or suspected autoimmune diseases (see Appendix 4). Patients with vitiligo, type I diabetes, or residual hypothyroidism caused by autoimmune thyroiditis that only requires hormone replacement therapy or is unlikely to recur in the absence of external stimulation can be enrolled
8. Have used corticosteroids (> 10 mg/day prednisone or equivalent dose) or other immunosuppressive agents within ≤ 14 days prior to the first dose of study drug. In the absence of active autoimmune diseases, inhaled or topical use of steroids and adrenal replacement steroids is permitted
9. Patients who have received or plan to receive live vaccines within 4 weeks prior to the first dose of study drug
10. With interstitial lung disease (ILD), drug-induced pneumonitis, radiation pneumonitis requiring steroid treatment, active pneumonitis with clinical symptoms, or severe pulmonary dysfunction
11. Patients with TB or history of active TB infection within ≤ 48 weeks before screening, regardless of treatment status
12. Except for alopecia and fatigue, other toxicities caused by previous anti-tumor treatments should have recovered to CTCAE 4.03 Grade ≤ 1 prior to the first dose of study drug. Patients with other toxicities caused by previous anti-tumor treatments that cannot be resolved within expectations and have long-lasting sequelae, such as neurotoxicity caused by platinum-based treatments, are allowed to be enrolled
13. Imaging (CT scan or MRI) showed tumor invasion of large blood vessels, symptoms of hemoptysis of daily hemoptysis ≥ 2.5 mL within 3 months before screening
14. Patients who have undergone minor surgery (including catheterization) within 48 hours before the first dose of study drug
15. Currently or recently (within 10 days prior to the first dose of study drug) using aspirin (> 325 mg/day) or other non-steroidal anti-inflammatory drugs known to inhibit platelet function
16. Currently or recently (within 10 days prior to the first dose of study drug) being treated with full-dose oral or parenteral anticoagulant or thrombolytic agents. But prophylactic use of anticoagulants is allowed
17. Patients with hereditary bleeding tendency or coagulation dysfunction. Patients with clinically significant bleeding symptoms or a clear bleeding tendency within 12 weeks prior to screening, such as hemorrhage of digestive tract, stomach ulcer with hemorrhage, baseline fecal occult blood++ and above, or vasculitis

18. Had arterial/venous thrombosis within 24 weeks prior to signing of ICF, such as cerebrovascular accidents (including transient ischemic attacks, cerebral hemorrhage, and brain infarction), deep vein thrombosis, and pulmonary embolism
19. Uncontrolled hypertension (systolic blood pressure \geq 140 mmHg and/or diastolic blood pressure \geq 90 mmHg), a history of hypertensive crisis or hypertensive encephalopathy
20. With a history of the following diseases within 24 weeks prior to the signing of ICF: peptic ulcer, gastrointestinal perforation, corrosive esophagitis or gastritis, inflammatory bowel disease or diverticulitis, abdominal fistula, tracheo-esophageal fistula, or intra-abdominal abscess
21. With clinical symptoms or diseases of the heart that are not well controlled, such as: (1) NYHA Class II or above heart failure (2) unstable angina (3) myocardial infarction within 24 weeks (4) patients with clinically significant supraventricular or ventricular arrhythmia requiring treatment or intervention
22. Known to be allergic to drugs or excipients, known to have severe allergic reactions to any kind of monoclonal antibody
23. Patients complicated with other malignant tumors \leq 5 years before the first dose, except for cervical carcinoma *in situ*, basal cell or squamous cell skin cancer that can be adequately treated, local prostate cancer after radical resection, and ductal carcinoma *in situ* after radical resection
24. With evidence or history of psychiatric disorders, alcoholism, narcotics or drug abuse
25. Patients with positive HBsAg and HBV DNA exceeding the upper limit of normal (1000 copies/mL or 500 IU/mL) or positive HCV (HCV RNA or HCV Ab test shows acute/chronic infection); known history of positive HIV or known to have AIDS
26. Have received any other investigational drug or participated in other interventional clinical study within 4 weeks prior to signing the ICF
27. The investigator determines that the patient may have other factors leading to the discontinuation of the study, such as protocol incompliance, other serious diseases (including mental illness) requiring concomitant treatment, serious laboratory test abnormalities, accompanied by family or social factors that may affect the safety of the subject or the collection of data and samples

